### **1.7.2.2 Potential Risks**

The clinical, pre-clinical and emerging safety profile has not identified any risks that would preclude investigation of a RXC004 and nivolumab combination in an advanced cancer setting. At high exposures of RXC004 the preclinical toxicities that overlap with those commonly seen with PD-1 inhibitors are those that affect the gut mucosa.

Checkpoint inhibitors including anti PD-1, as well as antibodies directed against PDL-1 and CTLA-4, boost the endogenous immune responses directed against tumours. AEs seen with checkpoint inhibitors are frequently due to immune-mediated mechanisms and can occur in any organ system. The most commonly seen immune-mediated effects include GI effects (e.g. diarrhoea or colitis), pneumonitis, hepatic events, skin rashes and dermatitis and endocrinopathies (including hypo and hyper-thyroidism).

The safety of nivolumab administered as a single agent or in combination with ipilimumab in patients with mCRC was evaluated in the CHECKMATE-142 study (NCT02060188). For single-agent nivolumab, the most frequent SAEs reported in  $\geq 2\%$  of patients were colitis/diarrhea, hepatic events, abdominal pain, acute kidney injury, pyrexia, and dehydration. The most common AEs reported in monotherapy (in  $\geq 20\%$  of patients) were fatigue, diarrhoea, pyrexia, musculoskeletal pain, abdominal pain, pruritus, nausea, rash, decreased appetite, and vomiting. {Overman, 2017 Ref 34}

Immune-mediated AEs that can occur during treatment with nivolumab can be seen weeks or months after discontinuation of treatment. Symptoms of these events will be monitored throughout treatment (e.g. diarrhoea, rash, and neuropathy). Laboratory assessments will check for elevated liver enzymes, kidney and thyroid function, electrolytes, glucose and blood counts.

A detailed description of the chemistry, pharmacology, efficacy, and safety of nivolumab is provided in the nivolumab prescribing information.

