### 5.2 Module 1 – RXC004 Monotherapy

The reason for conducting this study module is to provide the first cancer patient safety and tolerability data with RXC004.

Treatment, conduct, and withdrawal, which include starting dose and the dose escalation scheme, can be found in Section 3.1.2

Module 1 will commence by enrolling patients with advanced solid tumours into a SAD/MAD monotherapy dose-escalation arm. Eligible participants will be enrolled in sequential cohorts treated with RXC004 given as an oral capsule dose while being monitored for safety and DLTs.

Dose levels will not be weight-adjusted and the starting dose for the study will be RXC004 0.5 mg QD on Days 1-21 inclusive (for Cycle 1 and subsequent cycles). Dose increments will be guided by safety data observed during Cycle 1, as well as on-going assessment of safety beyond

Cycle 1 in earlier cohorts, plus PK and pharmacodynamic data as available. Every new dose cohort will be evaluated for the occurrence of a DLT during Cycle 0 or Cycle 1 of treatment. Patients will receive a single dose of RXC004 (Cycle 0) followed by a washout period (6-10 days) before receiving 21 continuous days dosing of RXC004 capsules (refer to Figure 4).

Module 1 will evaluate the safety and tolerability of RXC004 as monotherapy to provide dose(s) and schedules(s) for further modules, each evaluating the safety and tolerability of a specific combination agent. Module 1 will also provide preliminary efficacy readouts.

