## **5.3 Module 2 – RXC004 and Nivolumab Combination**

Based on the safety profile observed to date, a decision has been made by Redx and the SRC to start Module 2.

The reason for conducting this study module is to provide the first cancer patient safety and tolerability data with RXC004 in combination with nivolumab.

Module 2 will commence by enrolling patients with advanced solid tumours into a SAD/MAD monotherapy dose escalation arm. Eligible participants will be enrolled in dose-escalation cohorts treated with RXC004 given as an oral capsule dose in combination with a PD1 infusion. The dose of nivolumab will be a fixed dose of (480 mg every 4 weeks, and will remain at this dose level throughout the study. The dose of RXC004 will be escalated. The RXC004 starting dose for combination with nivolumab will be a lower dose than the highest confirmed safe and tolerated dose from the monotherapy study (Module 1). The RXC004 dose will be dose-escalated to the MTD in combination in as few dose-cohorts as possible. The RXC004 dose

used in Module 2 will not be escalated to exceed the MTD for RXC004 in monotherapy (2mg RXC004 QD).

Patients will take a single dose of RXC004 to evaluate single dose PK, then start on continuous RXC004 dosing up 3-7 days later in combination with nivolumab every 28 days (Cycle 1).

Each cycle will be 28 days from Cycle 1, Day 1.

Dose increments will be guided by safety data observed during Cycle 1, as well as on-going assessment of safety beyond Cycle 1 in earlier cohorts, plus PK and pharmacodynamic data as available. Every new dose cohort will be evaluated for the occurrence of a DLT during Cycle 0 or Cycle 1 of treatment. (Figure 5)

[figure not shown]
Patients will have the option to have their tumour tissue (primarily from an archival source) tested for genetic aberrations (including upstream Wnt pathway aberrations such as RNF43 mutations and RSPO-fusion) by next generation sequencing (NGS) or MassArray technologies.

RXC004 will be administered orally in combination with anti PD1 infusion in patients with advanced solid malignancies. There will be escalation of the RXC004 dose in each cohort with intensive safety monitoring to ensure the safety of the patients. The design of this Module 2 also allows the RXC004 & anti-PD1 combination tolerability and PK to be characterised in an unselected population of patients.

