### 9.2 Statistical Methods

All analyses, summaries, and listings will be performed using SAS® software (version 9.3 or higher). Modules will be summarized separately.

A baseline assessment will be defined as the last assessment performed prior to the first dose of study treatment. While many of these assessments will be performed on the day of the first dose, others will be performed during screening. If a patient is missing an assessment typically performed on the day of the first dose, screening values may be substituted as baseline.

Patient disposition, demographics, and baseline characteristics will be summarised using descriptive statistics.

In general, all efficacy, safety, and PK variables will be summarised using descriptive statistics. Continuous variables will be summarised by descriptive statistics (sample size [n], mean, standard deviation [SD], median, minimum and maximum). Categorical variables will be summarised in frequency tables (n, frequencies, and percentages). Individual subject data will be presented in listings. Missing data will not be imputed unless otherwise stated

The study data from each module will be analyzed and reported based on all patient data up to the time when all module patients have completed at least 6 cycles of treatment or have discontinued study treatment. Data will be listed, summarized, and analyzed by dose level and overall.

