## 9.6 Safety

### 9.6.1 Adverse Events

Treatment-emergent adverse events are defined as AEs that first occurred or worsened in severity after the first administration of the study drug and within 30 days of last dose of RXC004 in the case of module 1 and within 90 days of last dose of nivolumab for module 2. Adverse event summaries will include incidence of treatment-emergent AEs by MedDRA preferred term and system organ class, SAEs including deaths, AEs that led to study drug discontinuation, AEs leading to death, treatment related AEs and AEs by maximum severity..

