- i Consenting patients will have a 10 mL blood sample taken for preparation of a germ-line DNA sample at Screening (recommended time-point only).
- j CT (preferred) or MRI, each preferably with IV contrast. It is strongly recommended to maintain use of the same imaging modality (CT or MRI), acquisition protocol, facility and scanner across all imaging time points per patient. Note that where there is a rationale for assessment of bone lesions that develop after study start, these assessments will be performed as part of the CT or MRI assessment and will not require additional radiological bone scan assessment. Additional scans may be performed to confirm a Complete Response (CR) or Partial Response (PR) or disease progression (PD) as per appropriate response assessment guidelines. Any requirement for confirmatory scans will typically be performed at the next protocolled assessment time point. Other assessments e.g. whole body MRI or PET, are not protocol mandated, but may be performed as clinically indicated and at request of Investigator.
- k 480mg IV infusion over 60 minutes, q4w +/- 3 days, unless an infusion needs to held due to an adverse event. Results for chemistry, haematology and thyroid function labs must be available before commencing an infusion (within 3 days) and reviewed by the treating physician or Investigator prior to dosing. If a patient continues in the study on nivolumab alone, this treatment may be continued for a maximum of 12 months in total.
- l Follow up assessments should be performed 30 days after discontinuation of IP and 90 days after last dose of nivolumab
- m T3 and T4 will only be measured if TSH is abnormal or if there is clinical suspicion of an AE related to the endocrine system
- n For patients with Wnt ligand dependent tumours only (RNF43/RSPO aberrations or biliary/thymus cancers).

- o All patients must receive denosumab before first dose of RXC004. 120 mg sc denosumab should be administered approximately once every month from C0D1 until RXC004 discontinuation. Investigators may delay subsequent denosumab doses until the next scheduled visit providing that there is no significant increase in  $\beta$ -CTX compared to baseline, according to Investigator judgement

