Blood sample ctRNA analysis e			X		X	X	X		
RECIST 1.1 assessments (by CT/MRI) j		X	Every 6 weeks +/- 1 week from Cycle 1 Day 1 until RECIST1.1 defined disease progression						
Vitamin D3 and Calcium supplements		Patients should commence vitamin D3 (cholecalciferol 800IU QD) and calcium 1000-1500 mg QD supplements from ICF signature until RXC004 discontinuation							
Denosumab dosing o		120 mg sc. denosumab QM from C0D1 until RXC004 discontinuation							
RXC004 dosing			X	2 mg QD intermittent schedule k					
RXC004 PK f			X	X	X	X	X		
Concomitant medication		X	X	X	X	X	X	X	
Adverse events		X	X	X	X	X	X	X	
Taste Assessment m		X	At each visit – only if patient reports a taste disturbance						
Patient diary card review				X	X	X	X		
Subsequent anti-cancer therapy							X	X	X

Footnotes - General

Assessments made on Day 1 of each cycle are to be conducted prior to RXC004 administration, unless specified otherwise.

Additional assessments may be conducted as clinically indicated.

A tolerance of +/-1 day will be permitted for all study visits and a tolerance of -1 day for all assessments relative to the study visit, unless specified otherwise.

\* Female patients, if fertile, will require a serum pregnancy test at Screening and urine pregnancy on Day 1 of each cycle

\*\*Eligibility criteria to be re-checked at Cycle 1 prior to dose administration.

\*\*\*A lateral T & L spine assessment if a Vertebral Fracture Assessment (VFA) cannot be completed locally

- a A full physical examination is required at Screening and prior to Day 1 of each cycle ; Symptom-directed physical examination is acceptable at other time-points
- b Vital signs (heart rate, BP, temperature and respiration rate) will be assessed pre-dose and up to 1 hour after the RXC004 administration. Patient status will be monitored during RXC004 administration and repeat vital signs will be taken if needed. Height is required at screening only. Weight will be recorded at Screening and on Day 1 of each cycle.
- c All samples should be collected pre-dose
- d Fresh blood samples to be collected from UK sites only. All samples should be collected pre-dosing.
- e Samples should be collected pre-dose for all samples.
- f Patients will have PK blood sampling conducted at the following sample times
  - Cycle 0: Day 1 - Predose, then 30 mins, 1 h, 2 h, 4 h, 6 h, 8 h, 10 h, 12 h, 24 h, and 48 h post-dose.

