## 3. Disease Control Rate (DCR)

Disease control rate is defined as the proportion of all patients dosed that have a visit response of at least SD, PR, or CR at the second schedule scan post baseline, scheduled at week 12 for module 1 and module 3 or week 16 for module 2. Therefore, earlier visit responses of CR, PR that become PD at the second post baseline scan or NE responses at the second post baseline scan do not constitute disease control. A time window of 1 week around the visit will be applied and any visits occurring within 1 week of the scheduled time will be acceptable for inclusion in the assessment; however, if an earlier visit is defined as PD, then the visit response at the second post baseline scan would also be defined as PD. If the second post baseline scan is missing or NE, but the next evaluable response is SD or better, then the patient will be defined as having non-progressive disease at the second post baseline scan visit. Disease control rate will also be assessed separately for the first 3 scheduled post baseline scans (i.e., 18 weeks for module 1 and 3 and 24 weeks for module 2. A separate line in the ORR table will be presented to show the DCR for the

first 2 scan visits and DCR for the first 3 scan visits.

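### The module data cut in protocol 9.2 leaves no time for the 30- or 90-day adverse-event window, so treatment-emergent event counts are incomplete for patients who stop shortly before the cut

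*Protocol*

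**What the plan says.** Protocol 9.2 (Statistical Methods) bases each module's analysis and report on "data up to the time when all module patients have completed at least 6 cycles of treatment or have discontinued study treatment". This sentence fixes which data are included, not only when work on the report may start.

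The safety analysis looks further ahead. Protocol 9.6.1 counts treatment-emergent events "within 30 days of last dose of RXC004 in the case of module 1" and up to 90 days after the last nivolumab dose in Module 2. SAP IX.B repeats this and puts Module 3 with Module 1 at 30 days. Visits are scheduled to match. For Module 2, Appendix 2 footnote l reads "Follow up assessments should be performed 30 days after discontinuation of IP and 90 days after last dose of nivolumab". Appendix 9 footnote l sets a visit 30 days after the last RXC004 dose for Module 3. Both schedules allow 3 days either side.

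For efficacy, SAP VIII.A.3 adds a second, later disease control rate: "Disease control rate will also be assessed separately for the first 3 scheduled post baseline scans", that is, week 18 in Modules 1 and 3 and week 24 in Module 2, with a 1-week window. In Module 3 scans are due "Every 6 weeks +/- 1 week from Cycle 1 Day 1 until RECIST1.1 defined disease progression". Module 2 uses the same window every 8 weeks.

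SAP VI.G, the section on timing of analyses, gives no data cut-off. Neither document describes an update of a module report.

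**The concern.** Safety and tolerability are the primary objective (protocol 1.9.1). The protocol defines a post-treatment period over which events count and schedules visits to collect them, yet the reporting rule closes the data without waiting for that period. Protocol 1.7.2.2 says that nivolumab's immune-mediated events "can be seen weeks or months after discontinuation of treatment", so in Module 2 the truncated period is one in which the protocol itself expects events.

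If the rule is followed, patients who stop late contribute fewer days at risk than the TEAE definition implies, and a reader of the module tables cannot see this. The modules are small. In a six-patient Module 3 arm, one patient is 1/6 = 17% of the arm.

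**Working it through.** **Inputs**
- Cut rule: protocol 9.2.
- Cycle length: 21 days in Module 1 (protocol 5.2) and Module 3 (5.4.4). Module 2: "Each cycle will be 28 days from Cycle 1, Day 1".
- Scans: every 6 weeks (Modules 1 and 3) or 8 weeks (Module 2), +/- 1 week, counted from Cycle 1 Day 1 (Appendices 1, 2 and 9).
- TEAE window W: 30 days from last RXC004 (Modules 1 and 3), 90 days from last nivolumab (Module 2).
- Dosing days (5.4.4): 4 on/3 off weekly in Arm 1, 2 weeks on/1 week off in Arm 2. Nivolumab is given on Day 1 of each 28-day cycle.

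Days below are days after Cycle 1 Day 1, on nominal timing.

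**The plan's own scan times**
- 3 x 6 weeks = 18 weeks and 3 x 8 weeks = 24 weeks. Both match the stated times of the later disease control rate.
- End of Cycle 6: 6 x 21 = 126 days = 18 weeks; 6 x 28 = 168 days = 24 weeks. In every module, the nominal end of Cycle 6 is the nominal third-scan day.

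**TEAE window lost**

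Let g be the days from the last relevant dose to the cut. Days lost = max(0, W - g).

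Last patient stops at the end of Cycle 6:

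| Module | Last relevant dose | Cut | g | Days lost |
|---|---|---|---|---|
| 3, Arm 1 | Cycle 6 Day 18: 5 x 21 + 17 = 122 | 126 | 4 | 26 of 30 |
| 3, Arm 2 | Cycle 6 Day 14: 5 x 21 + 13 = 118 | 126 | 8 | 22 of 30 |
| 2 | Cycle 6 Day 1: 5 x 28 = 140 | 168 | 28 | 62 of 90 |
| 1 | Cycle 6 Day 21: 125 | 126 | 1 | 29 of 30 |

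SAP Table 3 lists only the 2 weeks on/1 week off schedule for Module 3, for which the figure is 22.

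Last patient stops earlier and so sets the cut: if the stop falls on a dosing day in Module 3, g is about 0 and essentially all 30 days are lost. In Module 2, with infusions on schedule, g lies between 0 and 28, so 62 to 90 days are lost. If nivolumab had already been withheld while RXC004 continued, g is larger and the loss smaller.

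**Who is not affected**

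Anyone with g of at least 30 (Modules 1 and 3) or 90 (Module 2) loses nothing. To illustrate, assume that Module 1's median exposure of about 7 weeks (protocol 5.4) applies, and take a patient who started with the one whose completion of Cycle 6 sets the cut. That patient stops near day 49, which is 126 - 49 = 77 days before the cut with 21-day cycles, or 168 - 49 = 119 days with 28-day cycles. Both exceed W. The documents give no enrolment dates, so the number of affected patients cannot be calculated.

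**Third scan**
- Windows: 126 +/- 7 = days 119 to 133; 168 +/- 7 = days 161 to 175.
- For a patient finishing Cycle 6 on the day of the cut, 7 of the 15 window days (127 to 133, or 169 to 175) fall after it.
- A patient who finished Cycle 6 more than 7 days before the cut has the whole window inside the data.

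**The case against.** Several points on the other side are sound and limit the reach.

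- **Few patients.** The cut waits for the last patient. Everyone who stopped well before it has full follow-up, and short exposure makes that likely for most. This stands. A reader might infer that the module's safety data are truncated generally; the arithmetic does not support that.
- **Not the whole window as a rule.** It is tempting to say that none of the 90 days is ever captured. Infusions are 28 days apart, so up to about 28 days may have elapsed. Total loss is the extreme case.
- **Safety oversight continues.** The Safety Review Committee decides on dose-limiting toxicities and later-cycle events as they emerge (protocol 3.2), SAEs are collected to 30 or 90 days (4.2), and events are followed to resolution (4.2.2). The defect lies in the reported counts, not in the escalation decisions. No hypothesis is tested, so no error rate is involved.
- **Disease control rate.** A reader might infer a general downward bias. Only patients finishing Cycle 6 in the final week and scanned late are exposed on nominal timing. Dosing delays move the end of Cycle 6 but not the scan calendar, which shrinks the loss. For a patient who completes Cycle 6, the main rate at week 12 or 16 is untouched.
- **Module 1.** Appendix 1 footnote 4 places scans in the 7 days before the end of Cycles 2, 4, 6 and 8, so before the cut, although the same table allows +/- 1 week. The SAP Introduction says Module 1 was already locked when the Module 2 and 3 changes were made.
- **Which cohort, and what sets the cut.** The documents do not establish that the affected patients belong to the last dose cohort, since cohorts can be expanded or doses de-escalated. Nor does a short median exposure show that a discontinuation will set the cut.

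None of this supplies the missing allowance. The sponsor may intend to wait for follow-up, but the text does not say so.

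**Conclusion.** The point holds in limited form. Protocol 9.2 closes the data before the TEAE window ends for any patient whose stopping sets the cut and for any whose last relevant dose was within 30 days (Module 3) or 90 days (Module 2) before it. For a last patient stopping at the end of Cycle 6, the loss is 22 to 26 of 30 days in Module 3 and 62 of 90 in Module 2, and more for an earlier stop. The secondary loss, up to 7 days of the third-scan window, matters mainly in Modules 2 and 3 and only for the supplementary week 18 or 24 rate.

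This rests on nominal cycle timing, on infusions given on schedule, on counting discontinuation from the day the patient stops rather than from the last dose, and on reading 9.2 literally. It does not show that most patients are truncated, that dose decisions were compromised, or that disease control is materially understated.

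**What to change.** For Modules 2 and 3, keep the trigger in 9.2 and state, there and in SAP VI.G, that the data cut is the later of:

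1. closure of the third-scan window (week 19 in Module 3, week 25 in Module 2) for every patient still being followed for progression; and
2. for every patient who has discontinued by the trigger date, whether before or after completing 6 cycles, completion of the 30-day follow-up (Module 3) or of both the 30-day and the 90-day post-nivolumab follow-up (Module 2), including the +3-day visit window, or death, withdrawal of consent or loss to follow-up.

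Add that TEAE follow-up is ongoing, and will be reported as such, for patients still on treatment at the trigger. Condition 2 must cover patients who stop after six cycles; otherwise someone who completes Cycle 6 and stops just before the cut is still truncated.

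The cost is wording and time, with no new visits. Condition 2 delays reporting by up to about 30 + 3 = 33 days (Module 3) or 90 + 3 = 93 days (Module 2). Condition 1 takes longer only if the last-enrolled patient stops early without progression and stays in scan follow-up. For a stop on day d, the wait is 133 - d or 175 - d days, which exceeds 33 or 93 only when d is below day 100 (133 - 33) or day 82 (175 - 93). If that delay is unwelcome, condition 1 could be limited to patients on treatment at the trigger, with the limitation stated.

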## Analysis Populations

Four analysis populations will be defined for use with various analyses.

- The Safety Population will consist of all patients who enrolled and receive at least one dose of study drug.
- The PK Evaluable Population will consist of those patients deemed by the sponsor or pharmacokineticist to have sufficient PK concentration data to be meaningfully included in the PK analysis summaries.
- The PD Evaluable Population will consist of those patients deemed by the sponsor or translational scientist to have sufficient PD assessment data to be meaningfully included in the PD analysis summaries.
- The Efficacy Evaluable Population will include patients who receive a radiographic assessment at baseline, received at least one dose of study treatment, and at least one post-dose radiographic tumour assessment, or progressed ahead of the first scan.

Adverse events and medical history will be coded using the Medical Dictionary for Regulatory Activities (MedDRA) version 20.0 or greater. Concomitant medications will be coded using the World Health Organization Drug Dictionary (WHODrug: March 2017 or later version).

